7.3. Recruitment

Research Assistants (RAs) within their respective clinical service will recruit help-seeking clients who are being cared for and supported within clinical services. The RAs will identify young people who potentially meet eligibility criteria via reviewing medical records of new referrals, consulting with clinicians working in the recruiting clinics and/or sitting in on clinical review at the respective recruitment sites or other site-appropriate study recruitment activities. This method closely aligns with other studies recruiting this clinical population. Initial suitability will be established by the fact that the young person appears to meet CHR criteria, falls within the targeted age range, appears competent to consent to the study, and there is no obvious indication that he/she meets exclusion criteria. Healthy control participants will be recruited from the community using a variety of methods, including social media posts and word of mouth as well as from an existing list of HC participants in previous studies who have indicated they would like to participate in future research projects.

7.4. Inclusion Criteria

Only participants who meet all of the inclusion and none of the exclusion criteria will be eligible to participate in the study.

Inclusion criteria for all participants (CHR and HC):

A participant will be considered eligible for inclusion in this study only if all of the following criteria apply:

- (1) Aged 12-30 years inclusive
- (2) Understand and sign informed consent/assent
- (3) Meet either CHR or HC criteria (see below for more details)

Specific inclusion criteria for CHR participants:

The participant must be help-accepting and meet diagnostic criteria for CHR (Vulnerability Group; Attenuated Psychotic Symptoms Group; Brief Limited Intermittent Psychotic Symptoms Group), as defined using the PSYCHS.

Specific inclusion criteria for HC participants:

HC will be matched with the sex, age, parental socioeconomic status and parental education level of CHR participants enrolled at each site. HC participants must not meet any of the exclusion criteria and must not:

1. Meet CHR criteria or have a current or past Cluster A personality disorder
2. Be receiving any current treatment with psychotropic medication
3. Have a family history (in first-degree relatives) of psychotic spectrum disorders, operationalised using the FIGS.

7.5.Exclusion Criteria

1. Antipsychotic medication exposure equivalent to a total lifetime haloperidol dose of >50 mg (see Appendix A for haloperidol equivalents), estimated based on available information (e.g., medical file documentation, patient and family report). If potential participants are on antipsychotic medication at the time of study screening, they can be titrated off this medication prior to study enrolment.
2. Documented history of intellectual disability.
3. Past or current clinically relevant central nervous system disorder. When necessary, Research Assistants will consult with study team investigators (including medical personnel) to determine if the central nervous system disorder is deemed to be clinically relevant.
4. Traumatic brain injury that is rated as 7 or above on the Traumatic Brain Injury (TBI) screening instrument.
5. Current or past treated or untreated psychotic episode, as determined using the PSYCHS.

7.6.Discontinuation and Withdrawal

7.6.1. Participant Discontinuation Criteria

A participant will be discontinued when the PI, Sponsor or HREC have decided that the participant will not complete the study. The status 'discontinued' is required to be documented. Discontinuation could include:

- (1) Participation interferes with the appropriate clinical management of risk to self or others.

- (2) An adverse event or serious adverse event leads to a request for discontinuation by an investigator or research member. These cases may be offered treatment as inpatients or via intensive community care, as per early psychosis guidelines. Data collected after meeting the discontinuation criterion will not be included in the primary analysis.

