5.5.1. Primary outcome

The primary outcome of interest is conversion to psychotic disorder by 24 month follow up (definition in 5.4).

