Participants from both samples will be assessed at Baseline. Refer to Section 8.0 for a full list of the measures and their explanation. The CHR sample will be followed up at regular intervals (see 8.0) for a total period of two years. A two year follow up period has been found to capture most CHR cases who convert to psychotic disorder⁹¹. Contact will be made with CHR participants between assessment time points (via phone calls, text messages or emails) in order to maintain engagement and address any technological troubleshooting issues with the digital momentary assessments. It is intended that if CHR participants are unable to be re-interviewed, their diagnostic status at last clinical contact will be sourced from their medical record files and state medical records (the client management interface [CMI] database for Victoria, Australia or local equivalent). HC participants will be assessed at baseline, at 2-month follow up, and at 12-month and 24-month follow up (see section 8.0).

The **screening visit** will take approximately 2 hours to complete. The **full baseline assessments** will take approximately 9–10 hours to complete (3-4 hours for clinical assessments, 1 hour for neurocognitive assessment, 2 hours for neurophysiological

assessments, 1.5 hours for neuroimaging, 20 minutes for free speech recording, and 30 minutes for blood). A saliva sample will be also be collected during one of the baseline visits. The baseline assessments may be completed over multiple sessions in order to minimise participant fatigue. There will also be a 30-min induction/information session at baseline for the digital momentary assessment component. The approximate duration of **follow up assessments** are as follows:

- **Months 1 and 3:** (90 minutes for clinical assessment)
- **Months 2:** 7.5 -8.5 (2-3 hours for clinical assessment, 45 minutes for neurocognitive assessment, 2 hours for neurophysiological assessment, 20 minutes for free speech recording, 30 minutes for blood, and 1.5 hours for neuroimaging)
- **Months 4, 5, 7, 8, 9, 10 and 11:** 20 minutes (BPRS clinical assessment only)
- **Month 6:** 2.5 hours (2 hours for clinical assessment and 30 minutes for neurocognitive assessment)
- **Month 12:** 3.5-4 hours (2.5-3 hours for clinical assessment, and 30 minutes for neurocognitive assessment)
- **Month 18:** 2 hours (clinical assessment)
- **Month 24:** 3.5 hours (2.5-3 hours for clinical assessment and 45 minutes for neurocognitive assessment)

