7.10. Withdrawal

All participants have the right to revoke consent from the study at any time and this will be clearly stated (verbally and in writing) at the time of consent. Withdrawal from the study can be at the request of the participant. Withdrawn participants will be informed that they will no longer continue with the study protocol and that their withdrawal from the study will not influence their treatment at clinical services. Participants who withdraw from the study will always be asked about the reason(s) for their withdrawal and about the presence of AEs. Adverse events that are possibly related to study procedures should be followed up until resolution, the adverse event stabilises or the participant is lost to follow up. The participant is not required to provide a reason of withdrawal. For a participant who withdraws their consent, their data collected up to the point of withdrawal will still be used for the purposes of the research unless explicitly stated by the participant that they wish their data removed from any applicable databases.

Withdrawal can include passive withdrawal of consent (participant not lost to follow up, but not attending scheduled appointments).

Every effort will be made to contact the participant, including use of all available contact details, and consulting with the relevant clinical teams. If the participant cannot be recontacted directly, it is intended that CMI (or the relevant local system) will be used to determine if the person has had contact with other mental health services. The study team will also ask the participant to nominate at least one friend or relative who can be contacted in the event that the participant cannot be contacted.

8. Visits and Assessments

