8.13. Data from other sources

If CHR participants are unable to be re-interviewed for the follow up assessments, their diagnostic status at last clinical contact will be sourced from alternative sources, such as medical record files and state medical records (e.g., the CMI database for Victoria, Australia).

9. Safety Measures

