9.2.1. Serious Adverse Event (SAE)

Hospital admissions which are related to an exacerbation in CHR symptomatology will not be reported as adverse events unless deemed to be causally related to the research activity.

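### Section 7.6.1 bars data obtained after an undefined discontinuation criterion from the primary analysis, so any later-captured 24-month conversion could not count

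*Protocol*

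**What the plan says.** Under 7.6.1, discontinuation is a decision of the PI, Sponsor or HREC. Two grounds are listed as things it could include, so the list is open. Ground (1) is: "Participation interferes with the appropriate clinical management of risk to self or others". Ground (2) is an adverse event or serious adverse event that leads an investigator or research member to request discontinuation. Still within ground (2) come two further sentences: "These cases may be offered treatment as inpatients or via intensive community care, as per early psychosis guidelines", and then the rule itself, "Data collected after meeting the discontinuation criterion will not be included in the primary analysis".

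Section 5.5.1 sets the outcome: "The primary outcome of interest is conversion to psychotic disorder by 24 month follow up". Section 7.2 treats it as a time-to-event outcome.

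Elsewhere the protocol tries to obtain outcome status when interviews fail. Section 6.4 says that "if CHR participants are unable to be re-interviewed, their diagnostic status at last clinical contact will be sourced from their medical record files", and 8.13 repeats that "their diagnostic status at last clinical contact will be sourced from alternative sources, such as medical record files". For participants who cannot be recontacted directly, 7.10 intends that "CMI (or the relevant local system) will be used to determine if the person has had contact with other mental health services". None of these sections says whether discontinued participants are included. Withdrawal of consent is handled separately in 7.10.

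**The concern.** There are two defects.

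First, the scope is unclear. Two analysts could build different primary datasets from 7.6.1, because there is no single criterion to apply. The cut is also dated from meeting the criterion, while the section separately requires the discontinued status to be documented; the two dates may differ.

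Second, the rule can remove primary-outcome data. The study is non-interventional, so no treatment comparison needs the cut, and withdrawal of consent does not explain it because 7.10 has its own rule. Events are the scarce resource for the prediction model: 7.2 counts on 300 in the combined networks, and 7.8 does not replace discontinued participants. If discontinued participants also went on to convert faster than the rest, censoring them would be informative. The estimated absolute risk would then be too low, and absolute risk is what the risk calculator in 15.3 is meant to give and what the calibration checks in section 14 assess.

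**Working it through.** **Reproducing the plan's figure.** Section 7.2 gives 937 + 1,040 = 1,977 CHR participants and a 15% conversion rate over 2 years. 1,977 × 0.15 = 296.6, which the protocol rounds to 300. PRESCIENT's share is 937 × 0.15 = 140.6.

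**What the protocol does not give.** It states no discontinuation rate, no conversion rate after discontinuation and no capture rate. All three are assumed here:
- 2% or 5% discontinued before conversion, at a constant rate over 24 months (19 or 47 of 937);
- hazard ratio HR of 1, 2, 3 or 5 for conversion after discontinuation;
- every later conversion captured;
- the rule applied in PRESCIENT only, since ProNET's text is not shown.

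**Model.** The conversion hazard is L before discontinuation and HR × L after it, the discontinuation rate is q, and T = 24 months. L and q are solved so that the share discontinued before conversion equals the assumed value and total 24-month risk is 15%.

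- Events lost per person = ∫₀ᵀ q·exp(−(L+q)s)·[1 − exp(−HR·L·(T−s))] ds
- Events lost in PRESCIENT = 937 × that value
- Pooled risk under the rule = the Kaplan-Meier limit with a fraction 937/1,977 of the cohort censored at discontinuation

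| Discontinued | HR | Events lost (of 297 pooled) | Pooled 24-month risk under the rule |
|---|---|---|---|
| 2% | 1 | 1.5 | 15.00% |
| 2% | 2 | 2.8 | 14.93% |
| 2% | 3 | 4.0 | 14.87% |
| 2% | 5 | 5.9 | 14.78% |
| 5% | 1 | 3.7 | 15.00% |
| 5% | 2 | 6.9 | 14.84% |
| 5% | 3 | 9.7 | 14.70% |
| 5% | 5 | 14.2 | 14.46% |

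Example at 5% and HR 5: L = 0.00621 and q = 0.00230 per month; loss per person 0.01519; 937 × 0.01519 = 14.2 events, or 14.2/296.6 = 4.8% of the pooled total. The implied later conversion among the discontinued runs from about 8% (HR 1) to 30-32% (HR 5).

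At HR 1 the risk stays at 15.0%: events are lost but a survival estimate is not biased. If only half of later conversions are captured, the events lost because of the rule halve to about 0.7-7.1. If none are captured, the rule costs nothing.

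**Which ground could select on the outcome.** Ground (1) concerns risk to self or others, so a link with worsening illness is conceivable. Ground (2) is narrower than it looks: 9.1 and 9.2 record adverse events only when possibly caused by study activities, and 9.2.1 adds that "Hospital admissions which are related to an exacerbation in CHR symptomatology will not be reported as adverse events" unless judged causally related to the research. The reference to early psychosis guidelines in ground (2) leaves a link to conversion open but does not show one. Note 2 to the schedule in 8.1 keeps converted cases in follow-up, so conversion does not itself trigger the rule, and conversions recorded before discontinuation are retained.

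**The case against.** The strongest reply is that the rule as printed is narrow and may cost almost nothing. It stands inside ground (2), which 9.1-9.2.1 restrict to study-related events. A discontinued participant is by definition not completing the study, so little may be collected afterwards. The look-up sections do not mention discontinued participants, and if they are not looked up, nothing is discarded. Record-based status is also a weaker source than PSYCHS criteria on severity, frequency and duration, and censoring at study exit is an ordinary choice. Section 14 describes itself as a broad outline and labels no analysis as primary.

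Much of this stands. It limits the size, makes the bias argument conditional, and justifies flagging record-based status by source. It does not remove the point. The exclusion is fixed in the protocol, so an analysis plan that counted these events would contradict it. The singular, undefined criterion remains whatever the page layout was.

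A reader might infer that the rule will discard conversions, or that it makes the 24-month risk too low. The documents support neither as an unconditional statement: loss requires that status be obtained after discontinuation, and bias requires faster conversion among the discontinued. A reader might also apply the rule to all 1,977 participants, where the same assumptions give 3.1-30.0 events lost and a risk of 13.85-15.00%. That needs the same sentence in ProNET's protocol; harmonised protocols and assessments, as 7.2 describes them, do not establish it.

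**Conclusion.** The point holds in limited form. The protocol fixes an exclusion whose scope cannot be determined from its wording and which, followed literally, keeps later-captured primary-outcome events out of the primary analysis without a stated reason. The certain consequence is loss of whatever conversions are captured after discontinuation. Understatement of risk is possible only under faster later conversion, and is less plausible if the rule reaches ground (2) alone.

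The size cannot be derived from the documents. On the assumptions above it is about 1.5-14 of 297 pooled events, with pooled risk moving by at most about 0.5 percentage points (15.00 − 14.46 = 0.54). That is probably small, but worth correcting because the repair is a few sentences.

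**What to change.** Replace the exclusion sentence in 7.6.1 with one stating that conversion status to month 24 obtained after discontinuation, within the participant's consent and subject to data removal under 7.10, counts in the primary analysis and is flagged by source (interview or records). State in 8.13 that the record look-up covers discontinued participants. Report censoring at the documented discontinuation date, whatever the ground, as a sensitivity analysis. The clinical grounds for discontinuation are not touched.

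Cost: a few sentences in 7.6.1 and 8.13, an HREC-approved amendment under 12.3, and possibly a consent-form change. The drawback is that status at last clinical contact is less exact and less precisely dated than a PSYCHS interview; the source flag and the sensitivity analysis let readers see how much the result depends on it.

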7.7. Study Discontinuation Criteria (Stopping Rules)

The study may be terminated at any time by the Sponsor.

7.8. Replacement of Participants

Participants who are withdrawn or discontinued from the study will not be replaced.

7.9. Incorrectly enrolled Participants

Incorrectly enrolled participants will be discussed by the Investigator and Orygen on a case-by-case basis, and a written decision will be made as to whether they should remain on study or be withdrawn.

7.10. Withdrawal

All participants have the right to revoke consent from the study at any time and this will be clearly stated (verbally and in writing) at the time of consent. Withdrawal from the study can be at the request of the participant. Withdrawn participants will be informed that they will no longer continue with the study protocol and that their withdrawal from the study will not influence their treatment at clinical services. Participants who withdraw from the study will always be asked about the reason(s) for their withdrawal and about the presence of AEs. Adverse events that are possibly related to study procedures should be followed up until resolution, the adverse event stabilises or the participant is lost to follow up. The participant is not required to provide a reason of withdrawal. For a participant who withdraws their consent, their data collected up to the point of withdrawal will still be used for the purposes of the research unless explicitly stated by the participant that they wish their data removed from any applicable databases.

Withdrawal can include passive withdrawal of consent (participant not lost to follow up, but not attending scheduled appointments).

Every effort will be made to contact the participant, including use of all available contact details, and consulting with the relevant clinical teams. If the participant cannot be recontacted directly, it is intended that CMI (or the relevant local system) will be used to determine if the person has had contact with other mental health services. The study team will also ask the participant to nominate at least one friend or relative who can be contacted in the event that the participant cannot be contacted.

8. Visits and Assessments

The Schedule of Assessments is shown in Section 8.1. An explanation of each measure can be found in the sections that follow. The aims of the research study will be best achieved if participants take part in *all* assessment components, as we are interested in building multimodal prediction models. Hence, participants must agree to participate in all assessments for which they are eligible. However, if a participant is ineligible to participate in a biomarker assessment (e.g., if they have braces and hence cannot undergo the MRI scan), they will still be able to participate in the study. The digital momentary assessments are an optional component of the study - participants can opt out of this component without compromising their participation in the overall study. The study visits may be split into multiple visits if this is preferred by the participant or the participant and their parent/legal guardian.

8.1. Table 2 Schedule of Assessments

✓ = CHR participants

C = HC participants (70 HCs - 20 from Melbourne, 5 from each of the other sites/hubs, will receive the repeat assessments at month 2 follow up)

		V1	V2	V3	V4	V5	V6	V7	V8	V9	V10	V11	V12	V13	V14	V15	V16	Conversion
Domain	Instrument/ Specimen	Screening	M0	M1	M2	M3	M4	M5	M6	M7	M8	M9	M10	M11	M12	M18	M24	
Informed consent																		
CLINICAL																		
Inclusion/Exclusion criteria	PSYCHS/SOFAS/SCID5-PD-Schizotypal /FIGS (abbreviated version)/ TBI/medication use (PharmaTreat)	✓C													C*		C*	
Medical & psychiatric history	Health and Medical Conditions Questionnaires	✓C	✓	✓	✓C	✓	✓	✓	✓	✓	✓	✓	✓	✓	✓C	✓	✓C	
Demographics	Demographics		✓C															
Premorbid functioning	PAS			✓														
Adverse events	Adverse Events		✓C	✓C	✓C	✓C	✓C	✓C	✓C	✓C	✓C	✓C	✓C	✓C	✓C	✓C	✓C	
Attenuated psychotic symptoms, associated distress, and conversion to psychosis	PSYCHS		✓C	✓	✓C	✓			✓						✓C*	✓	✓C*	✓C
General psychopathology	BPRS ⁹⁴		✓C	✓	✓C	✓	✓	✓	✓	✓	✓	✓	✓	✓	✓	✓	✓	
Depression	CDSS		✓C	✓	✓C	✓			✓						✓	✓	✓	
Anxiety	OASIS ⁹⁵		✓C	✓	✓C	✓			✓						✓	✓	✓	
Suicidality	CSSRS		✓C		✓C				✓						✓	✓	✓	

		V1	V2	V3	V4	V5	V6	V7	V8	V9	V10	V11	V12	V13	V14	V15	V16	Conversion
Sleep disturbance	PROMIS-SD		✓C		✓C				✓						✓	✓	✓	
Substance use	ASSIST ⁹⁶		✓C		✓✓				✓						✓	✓	✓	
DSM diagnoses	SCID-5-RVs ⁹⁷		✓C												✓C*	✓	✓C*	✓C
Patient global impression of severity	PGI-S		✓C	✓	✓C	✓			✓						✓	✓	✓	
Psychosocial functioning	SOFAS ⁹⁸ , GF Social, GF Role		✓C	✓	✓C	✓			✓						✓C*	✓	✓C*	✓C
Perceived Stress Scale	PSS		✓C	✓	✓C	✓			✓						✓	✓	✓	
Perceived Discrimination Questionnaire	PDQ		✓C															
Pubertal development Scale	PDS		✓C															
Psychosis Polyrisk Score	PPS ⁹⁹		✓C															
DIGITAL MOMENTARY ASSESSMENTS																		
Daily changes in mental state and context	EMA		✓C	✓C	✓C	✓C	✓C	✓C	✓C	✓C	✓C	✓C	✓C	✓C	✓C			
Physical activity, sleep-wake cycles, travel patterns	Passive sensing (actigraphy, geolocation)		✓C	✓C	✓C	✓C	✓C	✓C	✓C	✓C	✓C	✓C	✓C	✓C	✓C			
NEUROCOGNITION																		
Premorbid IQ	WRAT 5 Reading Accuracy		✓C															
		V1	V2	V3	V4	V5	V6	V7	V8	V9	V10	V11	V12	V13	V14	V15	V16	Conversion
Current IQ	WASI-II - 2-subtest version (Vocab & MR) ¹⁰⁰		✓C														✓	
Processing speed	Digit-Symbol Substitution Test		✓C		✓C				✓						✓		✓	

		V1	V2	V3	V4	V5	V6	V7	V8	V9	V10	V11	V12	V13	V14	V15	V16	Conversion
Attention	Continuous Performance Test		✓C		✓C				✓						✓		✓	
Working memory	Letter N-Back		✓C		✓C				✓						✓		✓	
Relational Memory	Digit-Symbol Substitution Test		✓C		✓C				✓						✓		✓	
Spatial memory	Visual Object Learning Test		✓C		✓C				✓						✓		✓	
Verbal learning	List Learning Test		✓C		✓C				✓						✓		✓	
Emotion recognition	Emotion Recognition Test		✓C		✓C				✓						✓		✓	
Motor	Finger Tapping Test		✓C		✓C				✓						✓		✓	
Sensorimotor speed	Motor Praxis*		✓C		✓C				✓						✓		✓	
NEUROPHYSIOLOGY (EEG)																		
Mismatch negativity/visual oddball	Mismatch negativity and visual oddball		✓C		✓C													
Auditory oddball	Auditory target/novelty P300		✓C		✓C													
	Auditory target/novel alpha desynchronisation																	
40 HZ auditory steady state response	40Hz inter-trial phase coherence, baseline inter-stimulus interval gamma power		✓C		✓C													
Resting state (eyes open/closed)	Power spectra 1/f slope		✓C		✓C													
BIOSECIMENS																		
Vital signs	Elevated body mass index, blood pressure, temperature		✓C		✓C													

		V1	V2	V3	V4	V5	V6	V7	V8	V9	V10	V11	V12	V13	V14	V15	V16	Conversion
Current health status and activity	Current illnesses and recent activity		✓C		✓C													
Elevations in white blood cells	Blood sample - CBC with differential		✓C		✓C													
Immune system, coagulation system, complement system, and oxidative stress	Blood sample - plasma, serum (multiplex, ELISA/mass spectrometry)		✓C		✓C													
DNA isolated for microarray/low-pass sequencing	Blood sample - buffy coat		✓C		✓C													
Functional assays for redox dysregulation and cell membranes for lipids (e.g. DHA/EPA/AA)	Whole blood sample (functional assays, mass spectrometry, gas chromatography)		✓C		✓C													
Cortisol	Saliva Collection (ELISA)		✓C		✓C													
SPEECH and FACIAL EXPRESSION																		
Language content and structure Speech acoustics	Free speech recording (Zoom audio)		✓C		✓C													
	PSYCHS interview recording		✓C	✓C	✓C	✓C			✓C						✓C	✓C	✓C	✓C
	Audio diaries recorded via smartphone as component of EMA (2 mins daily)		✓C	✓C	✓C	✓C	✓C	✓C	✓C	✓C	✓C	✓C	✓C	✓C	✓C			
Facial expression	Free speech recording (Zoom video)		✓C		✓C													
NEUROIMAGING (MRI)																		
Structural/functional (incl resting state)	T1, T2, diffusion MRI, resting state functional MRI (BOLD)		✓C		✓C													

		V1	V2	V3	V4	V5	V6	V7	V8	V9	V10	V11	V12	V13	V14	V15	V16	Conversion
TREATMENT AND HEALTH SERVICE UTILISATION	Psychosocial/ pharmacological treatment/service use		✓C	✓	✓C	✓			✓						✓C	✓	✓C	

Notes:

1. The Baseline visit needs to be conducted within 3 weeks of the screening visit. If not, the screening visit will need to be repeated. The study team will endeavour to schedule all other visits up to month 12 within +/- 1 week of their due date. For example, a Month 6 visit can occur up to 1 week prior to or after its due date. Month 18 and 24 will have a visit window of +/- 2 weeks. Assessments conducted outside these windows will be discussed with the local study team and the decision whether or not to utilize the data in analyses will be documented accordingly.
 2. Converted cases will be followed up as per the schedule of assessments. This will also be the case for participants who commence antipsychotic medication after study enrolment.
 3. Neurocognition tasks: Reading task in English speaking sites will be the WRAT5 Reading subtest; in non-English speaking countries the local version of the NART will be used. Apart from Premorbid and Current IQ, all other cognitive domains will be measured using the Web version of the Penn Computerised Neurocognitive Battery (PennCNB).
 4. The TBI will only be completed for participants where clinically indicated (i.e., participants who have had a traumatic brain injury, as reported by the participant or family or as determined from the participant's medical history).
 5. If conversion to psychosis is suspected based on the monthly BPRS assessment, then the PSYCHS and SCID will be conducted to check conversion status.
 6. Study participants will be contacted in between the formal assessments for the purposes of engagement and safety follow-up (see 8.12).
- * HC's will be contacted by Research Assistants at Months 12 and 24 and asked about their mood, behaviour, emotions, and other experiences since their last assessment (to determine possible onset of CHR status or psychiatric diagnosis). They will also be asked about any contact they may have had with mental health services since last visit. These check-ins will be completed using the PSYCHS, SOFAS, SPD, and the SCID 5 screening questions. If the SCID 5 screening questions indicate presence of a DSM 5 diagnosis, the relevant section of the SCID 5 will be completed. A full conversion to psychosis assessment will be administered if the PSYCHS indicates onset of psychotic disorder. These assessments will be conducted remotely (via phone or video call) and will take around 20-30 minutes. The Research Assistant can also provide a face-to-face visit if this is the preferred option.

